16. Appendices

16.1 Study Information

16.1.1 Protocol and Protocol Amendments

Note to File 21 October 2022

Note to File 20 October 2022

Note To File 30 September 2022

Final Protocol 30 August 2022

cerevance

NOTE TO FILE

To: Cerevance 424-102 Study Trial Master File

From: Consultant to Cerevance

Date: 21Oct2022

Study: CVN424-102

Re: Protocol Clarifications

The following are clarifications for the CVN424-102 protocol version 1.0 dated 30Aug2022.

- 9.1.5 Vital Sign Procedure
 - Clarifying that respiration rate is not needed in triplicate
 - Clarifying that the triplicate measurements at the "initial post-dose" timepoint are to be collected from 1-3 hours post administration of the study drug
 - Subsequent post-dose measurements (i.e., 24-, 48-, 72-, and 96- hours) are not needed in triplicate

Signed,

Consultant
Cerevance

NOTE TO FILE

To: Cerevance 424-102 Study Trial Master File

From: Consultant to Cerevance

Date: 20Oct2022

Study: CVN424-102

Re: Protocol Clarifications

The following are clarifications for the CVN424-102 protocol version 1.0 dated 30Aug2022.

The language in section 9.7.3 Reporting of Abnormal LFT, is to be updated as follows below. The rationale for the change is to better align with section 7.4 Criteria for Discontinuation or Withdrawal of a Participant.

Existing language:

If a participant is noted to have ALT or AST elevated >3 ×ULN on 2 consecutive occasions, the abnormality should be recorded as an AE at the discretion of the PI. In addition, an LFT increases eCRF must be completed by providing additional information on relevant recent history, risk factors, clinical signs and symptoms, and results of any additional diagnostic tests performed.

If a participant is noted to have ALT or AST >3 ×ULN and total bilirubin >2 ×ULN for which an alternative etiology has not been identified, the event should be recorded as an SAE and reported as per Section 9.7.2. The Investigator must contact the Medical Monitor to discuss the relevant participant details and possible alternative etiologies, such as acute viral hepatitis A or B or other acute liver disease or medical history/concurrent medical conditions. Follow up laboratory tests will be at the discretion of the Investigator.

To be replaced with:

If a participant is noted to have ALT or AST elevated >2 ×ULN at any point, the abnormality should be recorded as an AE.

If a participant is noted to have

[figure not shown]
- Alanine aminotransferase (ALT) or aspartate aminotransferase (AST) >8 × upper limit of normal (ULN), or
- ALT or AST >5 × ULN and persists for more than 2 weeks, or
- ALT or AST >3 × ULN in conjunction with elevated total bilirubin >2 × ULN or INR >1.5, or
- ALT or AST >3 x ULN with appearance of fatigue, nausea, vomiting, right upper quadrant

pain or tenderness, fever, rash and/or eosinophilia (>5%)

the event should be recorded as an SAE (note the reason for Seriousness: medically important event) and reported as per Section 9.7.2. The Investigator must refer to section 7.4 Criteria for Discontinuation or Withdrawal of a Participant for guidance as to the appropriate next steps.

Signed,

Cerevance

NOTE TO FILE

To: Cerevance 424-102 Study Trial Master File

From: Consultant to Cerevance

Date: 30Sep2022

Study: CVN424-102

Re: Protocol Clarifications

The following are clarifications for the CVN424-102 protocol version 1.0 dated 30Aug2022.

- Randomization: clarifying that Celerion will serve as designee for the randomization generation
- Physical Assessment at follow-up visit: clarifying that this is to be a symptom driven physical examination
- · Vital signs: clarifying that temperature is not needed in triplicate
- Appendix A: Schedule of Study Procedures
 - o Follow-Up:
 - Overall Study Day # to be update to 42
 - Randomization:
 - To be moved from first Check-in to first Dosing day
 - Pregnancy Test:
 - Add assessment to Day 5 of Period 3
 - C-SSRS:
 - Remove assessment from Day 1 of Periods 2 and 3 as well as from Follow-Up visit
 - o Physical Examination:
 - Add assessment to Day 2 of each Period for 24-hours post-dose
 - Vital Signs (footnote 3):
 - Update to include Respirations
 - Respirations should also be added to the Study Summary (page 11)
 - Urinalysis (footnote 5)
 - Update to include statement that Predose labs do not need to be reviewed prior to dosing
 - Clinical laboratory tests (footnote 7):
 - Partial list should be removed as Table 4 in section 9.1.11 indicates the full list of tests
 - ECG (footnote 11):
 - Study days to be updated to 0, 14, and 28
 - 3 hours post-dose window to be updated to +/- 30 minutes

Signed,

CVN424-102; CA38736; 16.1.1 Protocol and Protocol Amendments

Page 1 of 64 30 Aug 2022

PROTOCOL

2.0 STUDY SUMMARY

Name of Sponsor(s):	Compound:	
Cerevance Beta, Inc.	CVN424	
Title of Protocol: A Randomized, Open-Label, Single Oral Dose, Three-Way Cross-Over Trial to Evaluate the Relative Bioavailability of CVN424 Suspension and Tablet Formulations Including an Assessment of the Effect of Food on the Tablet Formulation in Healthy Adult Volunteers	IND No.: 138119	EudraCT No.: Not applicable
Study Number: CVN424-102	Phase: 1	

Study Design:

This is a Randomized, Open-Label, Single Oral Dose, Three-Way Cross-Over Trial to Evaluate the Relative Bioavailability of CVN424 Suspension and Tablet Formulations in Healthy Volunteers Under Fasted and Fed Conditions. The overall study design is outlined below:

Sequence	Dosing #1 (Period 1 Day 1)		Dosing #2 (Period 2 Day 1)		Dosing #3 (Period 3 Day 1)
1 (n=5)	Suspension (fasted)		Tablet (fasted)		Tablet (fed)
2 (n=6)	Tablet (fasted)		Tablet (fed)		Suspension (fasted)
3 (n=5)	Tablet (fed)	s h o u t	Suspension (fasted)	shout	Tablet (fasted)
4 (n=5)	Suspension (fasted)	W a s	Tablet (fed)	W a s	Tablet (fasted)
5 (n=5)	Tablet (fasted)		Suspension (fasted)		Tablet (fed)
6 (n=6)	Tablet (fed)		Tablet (fasted)		Suspension (fasted)

32 healthy male or female participants will be enrolled in 1 of 6 sequences (designated as 1 through 6, respectively) in an ascending fashion. Sequences 1, 3, 4, and 5 will have 5 participants each, and Sequences 2 and 6 will have 6 participants each.

Each sequence will proceed through the three cross-overs (suspension-fasted, tablet-fed, and tablet-fasted) according to the schematic above, with dosing to occur on Days 1 of Periods 1, 2, and 3. Participants in the fasted portion of each sequence will be dosed under overnight fasted conditions and will remain fasted for 4 hours post-dose. Water consumption is permitted as desired except for 1 hour before and after administration of the Study Drug.

To assess the effect of food on CVN424 bioavailability in tablet formulation, the single dose will be administered after ingestion of a standardized high-fat, high-calorie meal according to FDA Guidance for Industry (Food-effect bioavailability and fed bioequivalence studies, Jun 2022).

Page 10 of 64 30 Aug 2022

Participants for all sequences will be admitted to the study unit 1 day prior to dosing and remain in the unit for safety and pharmacokinetics (PK) assessments through 96 hours post-dose. The total confinement period will be 5 nights for each period unless extended at the discretion of the Investigator, e.g., for monitoring and/or management of adverse events (AEs).

Once 96-hour post-dose PK has been collected, participants will be discharged from the unit for the remainder of the washout period and return the day prior to their next scheduled dosing period.

Primary Objective:

To determine the relative bioavailability of 150 milligrams (mg) of CVN424 administered in a single dose of suspension formulation compared to 150 mg tablet.

Secondary Objectives:

To establish the effects of food on the rate and extent of absorption of CVN424 150 mg tablet when administered in fed conditions compared to administration under fasting conditions.

To assess the tablet's safety under fast and fed conditions and suspension under fasted conditions.

Exploratory Objectives:

To explore serum/plasma (e.g., potential characterization of drug metabolites) that may contribute to variability in CVN424.

To assess urine concentrations and volumes to enable calculation of urine PK parameters where possible.

Participant Population:

Healthy male and female participants 18 to 55 years old (inclusive)

Number of Participants:	Number of Sites:	
Estimated total: 32 participants (4 sequences of 5 and 2 sequences of 6)	1 (United States)	
Dose Level(s):	Route of Administration:	
Participants to receive a single-dose level of 150 mg CVN424 in either tablet or suspension formulation	Oral	
Duration of Treatment:	Period of Evaluation:	
Single oral dose on Day 1 of Periods 1, 2, & 3 (Study Days 0, 14,	Screening Period: up to 28 days	
& 28)	• 5 days of inpatient confinement from Check-In until after the 96-hour post-dose blood draw on Day 5	
	• 9 additional days of washout (Days 6-13)	
	To be repeated for the subsequent two Periods	
	Total Duration: Approximately 10 weeks	

Main Criteria for Inclusion:

Healthy male and female participants, 18 to 55 years of age, inclusive, and have a body mass index (BMI) between 18.0 and 35 kg/m² inclusive at Screening.

A complete list of inclusion criteria is provided in Section 7.1.

Main Criteria for Exclusion:

Participants are vegan, vegetarian, lactose intolerant, or follow a Kosher diet. Participants have a known hypersensitivity to any component of the formulation of CVN424. Participants have evidence of clinically significant [CS] neurologic, cardiovascular, pulmonary, hepatic, hematopoietic disease, renal, metabolic, gastrointestinal, urologic, immunologic, endocrine disease, serious allergy, allergic skin rash, psychiatric disorder, or other abnormality that may impact the ability of the participant to participate or potentially confound the study results. Any finding in the participant's medical history, physical examination, or safety laboratory tests gives reasonable suspicion of a condition

Page 11 of 64 30 Aug 2022

that might interfere with the conduct or interpretation of the study.

A complete list of exclusion criteria is provided in Section 7.2.

In addition, participants may not use any excluded medications, supplements, or food products. Concomitant medications and dietary products to be excluded are listed in Table 2.

Main Criteria for Evaluation and Analyses:

- Safety assessments:

Safety parameters will be collected from the signing of the informed consent form (ICF) until final charge and include AEs, clinical laboratory results, vital signs, physical examinations, and electrocardiogram (ECG).

- Vital signs will include body temperature measurement, blood pressure, and heart rate (beats per minute [bpm]).
- Orthostatic vital signs (blood pressure and heart rate) will be recorded
- Standard 12-lead ECG will be recorded. Clinical laboratory data collected will include hematology, chemistry, and urinalysis.
- Physical exams

A complete list of safety assessments is provided in Section 9.1, and the full Schedule of Study Procedures is provided in Appendix A.

- PK:

Plasma PK parameters will be used to determine the relative bioavailability of CVN424 suspension to tablet.

Plasma and urine samples will be collected for the determination of concentrations of CVN424 throughout the study as prescribed in the Schedule of Assessments (Appendix A).

PK parameters of CVN424 will be derived using noncompartmental analysis methods from the concentration-time data for all evaluable participants. Actual sampling times, rather than scheduled sampling times, will be used in all computations involving sampling times. The following PK parameters will be determined from concentrations of CVN424 in plasma: maximum observed plasma concentration (C_{max}), time to reach C_{max} (T_{max}), time taken for drug to appear in systemic circulation following administration (T_{lag}), area under plasma concentration-time curve (AUC) from time 0 to the last quantifiable concentration (AUC₀₋₁), and truncated AUC from time 0 to 96 hours (AUC_{0-96h}), AUCinf, terminal elimination half-life ($t_{1/2}$), apparent clearance after extravascular administration ($C_{L/F}$), apparent volume of distribution after extravascular administration (V_z/F) where possible

- Endpoints:

The primary endpoints of this study will be the following: the relative bioavailability of the CVN424 solution and CVN424 tablet formulation in the fasted state based on Cmax, Tmax, AUC_{inf}, and AUC_{0-96h}.

Additionally, the ratio of the PK parameters between CVN424 solution and tablet in the fasted state will be calculated and summarized descriptively. An analysis of variance (ANOVA) on log-transformed PK parameters (AUC $_{0-t}$, AUC $_{0-t}$, C $_{max}$) will be performed. Ratios of geometric means and 90% confidence intervals will be calculated. T_{max} will be compared between the CVN424 solution and the CVN424 tablet.

The secondary endpoints will be the following: The ratio of the PK parameters between CVN424 tablets in the fed and fasted state will be calculated and summarized descriptively. In addition, an ANOVA on log-transformed PK parameters (AUC0-t, AUC0- 96h, Cmax) will be performed. Ratios of geometric means and 90% confidence intervals will be calculated. Tmax will be compared between CVN424 tablets in the fed and fasted state.

The additional endpoints may include the following plasma PK parameters of CVN424: AUC∞ and t1/2z

Exploratory endpoints may include characterization of metabolic enzyme and transporter polymorphisms and/or qualitative metabolite identification in plasma and/or urine. Exploratory endpoints may also include renal PK parameters; cumulative amount of unchanged drug excreted into the urine (Ae), fraction of unchanged drug excreted in

Page 12 of 64 30 Aug 2022

the urine (fe), and renal clearance (CL_R).

Safety assessments will be measured by treatment-emergent adverse events (TEAEs), and tolerability will be measured by discontinuation (D/C) due to AE.

Statistical Considerations:

The proportion of participants administered CVN424 in tablet formulation who achieved at least an 80 percent relative bioavailability compared to CVN424 administered in suspension formulation as calculated by comparing the plasma drug concentration-time curves (AUC - area under the curve).

Safety:

AEs will be presented in listings, and TEAEs will be summarized. Individual results of laboratory tests (hematology, chemistry, and urinalysis) will be recorded at baseline and post-dose, and changes from baseline will be summarized using shift tables. Individual vital signs will be recorded and observed values and changes from baseline will be summarized. Individual results of quantitative ECG parameters from the 12-lead safety ECGs will be listed and observed values and changes from baseline will be summarized. All summaries will be performed by each sequence (suspension and table fasted and tablet fed separately), and CVN424 suspension versus tablet overall, and separately each of the 6 CVN424 sequences overall. Physical exam findings will be presented in data listings.

PK Analysis:

Noncompartmental pharmacokinetic (PK) calculations include C_{max}, T_{max}, and AUC_{0-96h} active ingredients.

Sample Size Justification:

It is planned to enroll 32 male or female participants for participation. Based on previous PK studies with CVN424, it was determined 28 participants would be needed to show bioequivalence, assuming an intra-participant CV of 16% and an expected ratio of 1:10. 32 participants will be enrolled to ensure at least 28 evaluable participants.

CVN424

Study No. CVN424-102 Page 13 of 64
Clinical Protocol Version 1.0 30 Aug 2022

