5.0 STUDY OBJECTIVES AND ENDPOINTS

5.1 Objectives

Objectives	Endpoints
Primary	Primary
To determine the relative bioavailability of 150 mg of CVN424 administered in a single dose of suspension formulation compared to 150 mg tablet.	 The relative bioavailability of the CVN424 solution and CVN424 tablet formulation in the fasted state based on maximum observed plasma concentration (C_{max}), time to reach C_{max} (T_{max}), and area under the plasma concentration-time curve from time 0 to 96 hours (AUC _{0-96h}). The ratio of the PK parameters between CVN424 solution
	and tablet in the fasted state will be calculated and summarized descriptively. In addition, an analysis of variance (ANOVA) on log-transformed PK parameters (AUC _{0-t} , AUC _{0-96h} , C _{max}) will be performed. Ratios of geometric means and 90% confidence intervals will be calculated. T _{max} will be compared between CVN424 solution and CVN424 tablet.
Secondary	Secondary
 To establish the effects of food on the rate and extent of absorption of CVN424 150mg tablet when administered in fed conditions compared to administration under fasting conditions. To assess the safety of the tablet under fast and fed conditions and suspension under fast conditions. 	• The ratio of the PK parameters between CVN424 tablets in the fed and fasted state will be calculated and summarized descriptively. In addition, an analysis of variance (ANOVA) on log-transformed PK parameters (AUC _{0-t} , AUC _{0-96h} , C _{max}) will be performed. Ratios of geometric means and 90% confidence intervals will be calculated. T _{max} will be compared between CVN424 tablets in the fed and fasted state. T _{max} and T _{lag} will be compared between CVN424 tablets in the fed and fasted states in the fed and fasted state.
	• Assessment of safety as measured by TEAEs and tolerability as measured by discontinuations (D/Cs) due to AE.
Exploratory	Exploratory
• Explore serum/plasma (e.g., potential characterization of drug metabolites) that may contribute to variability in CVN424.	Potentially characterize metabolic enzyme and transporter polymorphisms.

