11.3 Determination of Sample Size

It is planned to enroll up to 32 male or female participants for participation in this study.

Based on previous PK studies with CVN424, it was determined 28 participants would be needed to show bioequivalence, assuming an intra-participant CV of 16% and an expected ratio of 1.10. 32 participants will be enrolled to ensure at least 28 evaluable participants.

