8. SUMMARY OF CHANGES FROM PROTOCOL-PLANNED ANALYSIS

Screen failure data (demographics or reason for screen failure) will not be summarized though the protocol indicated that these would be summarized.

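### Does the synopsis's one-sided 80% responder proportion compete with the bioequivalence rule as the definition of the primary result?

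*Protocol*

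**What the plan says.** The Study Summary (Protocol 2.0) has a heading Statistical Considerations. Before its safety, PK and sample-size sub-parts there is one sentence without a main verb: "The proportion of participants administered CVN424 in tablet formulation who achieved at least an 80 percent relative bioavailability", compared with the suspension and based on AUC. It does not say which AUC is meant, whether the tablet is fasted or fed, or what proportion would count as success.

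The other relevant places are these:

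- **Study Summary (Endpoints) and Protocol 5.1.** The primary comparison is an ANOVA on log-transformed parameters, and "Ratios of geometric means and 90% confidence intervals will be calculated". The proportion does not appear, and neither do any equivalence limits.
- **Protocol 11.3.** "it was determined 28 participants would be needed to show bioequivalence", "assuming an intra-participant CV of 16% and an expected ratio of 1.10". The proportion plays no part.
- **Protocol 11.1 and 11.1.3.** Analysis variables and methods are left to the SAP for detail.
- **SAP 6.6.** Similar bioavailability is concluded if the 90% intervals for AUC0-t, AUC0-96h and Cmax fall inside 80.00 to 125.00%.
- **SAP Table 14.2.1.7 (shell CPR1).** Individual treatment ratios are listed and summarised, with no count at or above 80%.
- **SAP Section 8.** One departure is recorded: "Screen failure data (demographics or reason for screen failure) will not be summarized though the protocol indicated that these would be summarized". The proportion is not mentioned.

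**The concern.** Taken alone, the fragment reads like a success measure, and a bad one. Each participant takes one dose of each treatment, so an individual tablet/suspension ratio carries the within-participant error of two single observations. Some participants would fall below 0.80 even if the two products were identical. With no upper bound, a tablet that delivers too much would score better than one that matches the suspension.

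It is also a different quantity from an average ratio. If it were the primary result, the protocol would hold two definitions of success that can point in opposite directions, and the SAP would have discarded one without recording it.

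**Working it through.** **Inputs.** CV 16%, expected ratio 1.10, 28 evaluable and 32 enrolled (Protocol 11.3); cut-off 0.80 (Study Summary); limits 0.80 to 1.25 with a 90% interval, i.e. 5% per side (SAP 6.6).

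**Step 1: reproduce the plan's 28.** The log-scale within-participant SD is √ln(1 + 0.16²) = 0.1590. The standard error of the log mean ratio is 0.1590 × √(2/28) = 0.0425. Two one-sided tests at a true ratio of 1.10, integrated over the residual variance, have power 90.0% with 26 degrees of freedom (n − 2) and 90.7% with 52 (2n − 4). Under both, 28 is the smallest n that reaches 90%; for 80% power, 20 or 21 would do. The protocol does not state the power, but 28 reproduces at 90%. It was therefore derived for the average ratio. (The Study Summary prints the ratio as 1:10; only 1.10 gives 28.)

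**Step 2: behaviour of the proportion.** The SD of an individual log ratio is √2 × 0.1590 = 0.2248. For true ratio θ, the share below 0.80 is Φ((ln 0.80 − ln θ)/0.2248). At θ = 1.00 this is Φ(−0.2231/0.2248) = Φ(−0.992) = 0.1605, or 4.5 of 28 and 5.1 of 32. The last column is the chance that one parameter meets the SAP 6.6 criterion with n = 28 and 52 degrees of freedom.

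| True tablet/suspension ratio | Below 0.80 | At or above 0.80 | Meets SAP 6.6 |
|---|---|---|---|
| 0.90 | 30.0% | 70.0% | 86.2% |
| 1.00 | 16.0% | 84.0% | 99.96% |
| 1.10 | 7.8% | 92.2% | 90.7% |
| 1.25 | 2.4% | 97.6% | 5.0% |
| 1.40 | 0.6% | 99.4% | about 0.001% |

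The proportion climbs with over-delivery, while the SAP criterion rejects it.

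**Step 3: sensitivity.** The protocol does not tie the 16% to AUC. At θ = 1.00 the share below 0.80 would be 5.7%, 9.3%, 21.3% or 26.1% for an assumed CV of 10%, 12%, 20% or 25%. The one-sidedness does not depend on the CV.

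**Step 4: does anything use it?** The proportion is absent from the Study Summary's endpoints, Protocol Sections 5 and 11, SAP Section 2, SAP 6.6 and the table shells. No threshold is attached to it anywhere, so no product can pass or fail on it. The only decision rule for the formulation comparison is SAP 6.6. Anyone who wanted the count could read it from the individual ratios in Table 14.2.1.7.

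**The case for a change.** The best argument for a change is that the protocol never states the 80.00 to 125.00% limits. Section 5.1 asks for ratios and intervals but gives no bounds; these appear only in the SAP. The one-sided 80% is thus the only numerical bioavailability criterion in the protocol, and someone reading it alone could take it for the success measure. The trial is open-label with interim looks at plasma data, which makes a single clear criterion more desirable. SAP Section 8 exists to log departures and found room for a smaller one, the notes to file corrected lesser details, and the remedy is a sentence or two.

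The inconsistency is real and SAP Section 8 is incomplete. The step from there to a competing primary result does not hold. The fragment never calls itself primary, whereas the same Study Summary names the primary endpoints explicitly and leaves the proportion out. Protocol 11.1 hands methodology to the SAP, whose rule is two-sided and explicit. SAP Section 1 also commits the study report to documenting changes from the protocol's planned analysis, so an unlisted item has a place to be recorded.

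**Conclusion.** No change to the plan follows. The sentence is a drafting leftover in the synopsis, and removing or relabelling it would leave every estimate, interval and conclusion as it is.

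The criticism of the measure itself is sound: about 16% of participants below 0.80 for an identical product, and a score that improves to 97.6% at a true ratio of 1.25. Those figures assume that the 16% CV holds for AUC, that log ratios are normal, and that there is no participant-by-formulation interaction. At the planning ratio of 1.10, read as tablet over suspension, the share below 0.80 is 7.8%.

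The conclusion rests on SAP 6.6 being the rule applied. It would need revisiting only if the study report offered the proportion as evidence of similar bioavailability, which neither document plans.
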